## Results

- Results of the CT/NG testing will be available to the women after 90 minutes, placed in the medical record, and communicated to medical providers. Efforts will be made to provide results to participants on the same day.
- Results for syphilis will be available to women after 20 minutes, placed in the medical record, and communicated to medical providers. Efforts will be made to provide results to participants on the same day.

## Treatment

- Women diagnosed with CT will receive a single dose of oral azithromycin (1 gram) and women diagnosed with NG will receive a single dose of oral azithromycin (1 gram) and a ceftriaxone 250 mg injection will be administered on site according to standard of care per Botswana MOH guidelines.
- Infants testing positive will receive treatment according to Botswana guidelines (20mg/kg of azithromycin (liquid formulation) for CT, injection of 50mg/kg of ceftriaxone for NG) and referrals
- Women testing positive for syphilis either through the dual syphilis/HIV or rapid syphilis test will be counseled according to Botswana guidelines, including assessing previous syphilis diagnoses and treatment and penicillin allergies. Treatment will also be initiated according to national guidelines. As Botswana is a low syphilis prevalence setting (<5%), the national guidelines follow WHO recommendations and currently recommend Benzathine penicillin 2.4MU IM weekly for 3 weeks with alternative treatments for pregnant women with penicillin allergies. For women with reactive

Title: The diagnosis and treatment of *Chlamydia trachomatis* and *Neisseria gonorrhoeae* in pregnant women to prevent adverse neonatal consequences.”

treponemal tests, the standard of care RPR test titre results will be provided to the participant's physician to inform further treatment/management.

#### **Test of cure**

- A test of cure will be performed approximately four weeks after initial treatment for CT/NG during an antenatal care visit to document clearance of infection. If patients are positive on repeat testing, they will be retreated and given additional counseling regarding CT and NG and additional efforts will be made to follow up, counsel and treat any new sex partners or old sex partners who have not been treated.

#### **Partner Services**

- All study staff will be trained on appropriate and effective methods for counselling women on how to communicate test results to partner(s) (from the past 60 days) in a nonthreatening and blameless manner. (For example, it's important to clarify that the duration of sexually transmitted infections during pregnancy is unknown, many infections are asymptomatic, and infections do not have implications about partner fidelity). Additionally, participants will be given several options for partner services: 1) No disclosure: In the case of risk for intimate partner violence (IPV). 2) Supportive disclosure: where the participant is assisted by trained study staff either in person or over the phone in notifying their partners. Also, participants will be given the option of bringing partners to the study clinics for counselling and treatment. 3) Expedited partner therapy: where the participant can bring CT/NG treatment to partners prior to examination by a healthcare provider. IPV: will be proactively assessed and managed for all participants, not only those testing STI positive. To that end, we will use a validated screening tool adapted from Rabin RF et al. to assess participant risk for intimate violence and other negative partner responses to notification of an STI. Based on the screening results, when appropriate, IPV risk will be mitigated by referring women to local support services available in the country for free counseling and support, the NGO Botswana Family Welfare Association (BOFWA; <http://www.bofwa.org.bw/>). We will also provide a 24-hour emergency contact line through which participants can receive information and support and referrals in general.

- Efforts will be made to ensure that partners return to the study clinics for treatment. Those who return will receive the stat doses of azithromycin and ceftriaxone or Benzathine penicillin as described above for participants. In cases where participants and study staff are concerned about partner access to prompt clinical evaluation and treatment for CT/NG, partners will be offered expedited therapy (EPT) whereby participants will be provided with treatment to bring home for partner(s). For CT, EPT will consist of a single dose of oral azithromycin (1 gram). For NG, EPT will consist of oral cefixime (400mg) and a single dose of oral azithromycin (1 gram).

8. **Research involving survey, questionnaires:** There is a questionnaire for demographic data and medical history for participants that will be filled out by study staff and a brief semi-structured interview on partner notification and treatment experiences that will be conducted by study staff in a sub-set of participants.

9. **FDA approval (e.g. for experimental drugs, etc.)---- N/A**

Title: The diagnosis and treatment of *Chlamydia trachomatis* and *Neisseria gonorrhoeae* in pregnant women to prevent adverse neonatal consequences."

## **10. Data collection, Storage and Confidentiality:**

Data will be collected electronically using REDCap. Data stored in REDCap will not have personal identifiers and personal identification codes will be used. A code sheet linking the data to the subject's personal identification will be stored separately from the REDCap data in a locked research office in the BHP offices. Only authorized study personnel will have access to the REDCap data and the linking form. Each staff member will have their own secret login and REDCap logins will be monitored by the study manager.

## **11. Risk/Benefit Assessment (12-17)**

### **a. Potential Risks and Discomforts:**

The potential risks encountered during the study are: 1) CT and NG testing 2) Specimen collection. 3) Questionnaire. 4) Data analysis

#### **Conducted by Study Personnel at Princess Marina:**

The primary potential risks to participants due to study participation are psychological and social in nature. Physical risks from a self-collected vaginal specimen are negligible. Unlike HIV and syphilis testing, screening for CT or NG is not a routine part of the standard of care for pregnant women in Botswana, participants in the comparison group have no risk greater than that normally incurred during a typical antenatal care visit; i.e. mild physical or psychological discomfort. IPV is a possible risk when women test positive for CT/NG. IPV will be proactively assessed and managed for all participants using a validated screening tool to assess participant risk for intimate violence and other negative partner responses to notification of an STI. Based on the screening results, when appropriate, IPV risk will be mitigated by referring women to local support services available in the country for free counseling and support. We will provide a 24-hour emergency contact line through which participants can receive information and support and referrals in general. Also, women will be given several options for partner notification and treatment.

A. Psychological: Participants could experience psychological distress such as anxiety when discussing issues related to personal experiences, sexual health, or pregnancy. However, we do not expect any serious events to occur based on our experience across multiple previous studies, including our pilot study with this same population in Botswana. Participants may experience some stress related to the knowledge of STI status. Participants will be given information and education about the nature and consequences of all infections and treatment, and those testing positive (including newborns) will be provided treatment as per standard treatment protocols. The likely harmful consequences of learning one's STI status are low.

B. Social: Participation in this study may cause social harm (e.g., discrimination, false assumptions, rumors) if the participation of the participant becomes known to others. One of the more significant risks is notification of sexual partners about positive results of CT or NG testing, which is an important step to protect the health of the partners and their future contacts. It is possible that notifying partners about a positive CT or NG test could put the participant at risk for IPV. Given this, we will provide IPV prevention counseling and will take steps to mitigate and monitor such outcomes, providing intensive participant support as needed.

Title: The diagnosis and treatment of *Chlamydia trachomatis* and *Neisseria gonorrhoeae* in pregnant women to prevent adverse neonatal consequences."

C. Alternative treatments and procedures: Participants from the target population invited to participate will be able to decline participation, with no consequence to them.

**b. Risk Classification:** Minimal.

**c. Minimizing Risks:**

Informed consent and strict confidentiality will be rigorously enforced to minimize risks to participants and their partners. All study personnel will receive training in the informed consent process.

Additional protections will be put in place for participants under the age of 18 including reporting requirements for abuse and referrals to social workers and added support for partner notification. We have also added an adolescent health expert to our team to advise on adolescent-related issues.

Trained providers will be available in case participants have difficulty in any part of the specimen collection such as pain or discomfort or in the case of any adverse event.

Participants will be provided with a number whereby a member of the clinic staff and the Principal Investigator, [name], may be contacted to answer questions or in case of emergency or any questions regarding their informed consent.

**d. Potential Benefits:**

**Conducted by study personnel:**

Diagnosis and treatment of CT/NG may prevent the development of future complications in reproductive health as well as transmission of undiagnosed infections to newborns and sexual partners, and reduce the risk of adverse birth outcomes. Diagnosis and treatment of CT/NG may address symptoms among infants. Participants in the syphilis PoC testing clinics will have access to rapid syphilis results, which may increase the likelihood of treatment access for those who test positive and may reduce the need for non-routine follow-up visits.

Potential benefits to society include determination of the benefits (in terms of infections cured and prevention of vertical transmission of STIs and subsequent adverse outcomes) of integration of routine CT/NG screening into antenatal care in Botswana. The study will also provide valuable operational data regarding of patient follow-up and treatment, as well as insights into the formation and revision of antenatal care policies, guidelines and funding levels. Results will serve to estimate prevalence of CT/NG infections among asymptomatic pregnant women in Gaborone, Botswana.

**Risk/Benefit Ratio:** The benefits to the participants in diagnosis and treatment of CT/NG infection outweigh the risks of physical or personal discomfort from specimen collection. As syphilis testing is already part of the standard of care, there are no additional testing risks. As described above, confidentiality of study data will be rigorously maintained. The benefits of PoC syphilis testing include same day results and treatment.

**12. Therapeutic Alternatives:** Participation in the study protocol is voluntary. Patients declining participation will still receive treatment from their physician, including STI screening, according to current standards of care.

**13. Financial Considerations:**

Title: The diagnosis and treatment of *Chlamydia trachomatis* and *Neisseria gonorrhoeae* in pregnant women to prevent adverse neonatal consequences."

**a. Payment for Participation:** Participants will receive 50 Pula to help compensate for attendance at each study visit including baseline, test of cure, third trimester, postnatal, and infant testing visits.

**b. Financial Obligations of the Subjects:** There are no costs to participate in the study.

#### **14. Emergency Care and Compensation for Research-Related Injury:**

Minimal risk is associated with participation in this study. A telephone number is provided on the informed consent form for participants to speak with a study clinician if they believe they have experienced a research-related injury. Study personnel will help participants obtain appropriate care or direct them to the hospital's emergency room if they believe they have a life-threatening emergency.

#### **15. Informed Consent:**

**a. Capacity to consent:** All subjects will have the capacity to give informed consent.

**b. Personnel Inviting Participants:**

Study personnel will invite potential participants and will help them to understand the informed consent document. Only after all the information has been provided and the potential participants have all their questions about the study answered, will staff ask them to sign the informed consent form to participate in the study. The process of obtaining informed consent will be finished before collection of data or specimens. Study personnel will give a copy of the consent document to the participants to keep. They will exclude any potential participant who is unable to understand the informed consent, severely mentally disabled, or does not meet age criteria. They will keep consent forms in a locked office in Gaborone. All study staff involved in recruiting and consenting participants will have completed the Botswana equivalent of a Human Research Subjects certification program before the beginning of the study.

#### **16. Process of Consent:**

After verification of eligibility, the informed consent process is as follows:

- The study interviewer says: "We would like to read through this consent form with you because we want to make sure that you understand everything in it and that we answer any questions you may have." The study interviewer reviews the consent form, paragraph by paragraph, and stops as needed for any questions or clarifications.
- The interviewer asks the potential participant short questions about the consent to make sure that she fully understands the study. This process gives the interviewer time to assess the potential participant to make sure there are no "gross Impairments" that would invalidate the informed consent (e.g. participant does not fully understand the study, is intoxicated, etc.) and make study participation unethical and prohibited.
- If the potential participant agrees to participate in the study, the study interviewer then signs and dates the consent form. The participant's study code is then written on the consent form.
- The subject is given a copy of the consent form.

#### **17. Comprehension of the Information Provided:**

Title: The diagnosis and treatment of *Chlamydia trachomatis* and *Neisseria gonorrhoeae* in pregnant women to prevent adverse neonatal consequences."

The study personnel will ask participants to restate in their own words the study's objectives and what participation involves to determine if they fully understand the informed consent. If the participant does not understand the protocol, the study interviewer will explain again the content of the consent form. If the participant is still unable to understand the protocol after it is reviewed again, she will be excluded from participation in the study.

**18. Information withheld from Subjects:** Not applicable.

**19. Consent/Accent forms:** The consent form used in the study is in the appendix.

**20. Conflicts of Interest**

The investigators involved in this study have no conflicts of interest to report.

**21. Study Timeline**

Table 1: Study Timeline	Start	Finish	Duration
Component and Task Name			
I. Preparation and Piloting	Jan 2020	Dec 2020	12 mo.
II. Enrollment and Follow-up (CT/NG)	Feb 2021	Mar 2022	11 mo.
III. Enrollment (syphilis post-test group)	August 2022	Feb 2023	7 mo.
IV. Follow-up only (CT/NG)	Apr 2022	Dec 2022	9 mo.
V. Data Analysis and Dissemination	Jan 2023	May 2023	5 mo.

**22. Dissemination Plan:**

Test results and educational information will be shared with patients. Results of the study will be compiled into a report and presented to the Ministry of Health. Results will also be presented at local and international scientific conferences. Additionally, the study will be described in an article that will be submitted for publication in a peer-reviewed journal and results will be presented at national and international meetings. Finally, the results of the study will be shared with patients and staff at Gaborone City Clinics through presentations and posters.

Title: The diagnosis and treatment of *Chlamydia trachomatis* and *Neisseria gonorrhoeae* in pregnant women to prevent adverse neonatal consequences."

## APPENDIX

**Informed Consent and questionnaire are attached.**

Statistical Plan: Evaluating the diagnosis and treatment of *Chlamydia trachomatis* and *Neisseria gonorrhoeae* in pregnant women to prevent adverse neonatal consequences in Gaborone, Botswana

ANALYSIS

Primary outcome measure

- Mother-to-child transmission of CT and/or NG: Neonates of mothers who test positive for CT and/or NG infections will be tested using both ocular and nasopharyngeal specimens.

Secondary outcome measures

- Pregnancy outcome
 - o Miscarriage, defined as pregnancy loss before the 20th week of gestation, will be identified through self-report by the participants, and the medical record.
- Perinatal outcome
 - o Stillbirth, defined as fetal death at or after 20 weeks gestation and prior to delivery, will be identified through self-report by the participants, and the medical record.
- Neonatal outcomes
 - o Preterm birth, defined as delivery prior to 37 weeks' gestation, will be identified through the obstetric record and/or
 - o Low birth weight, defined as birth weight of less than 2500g, will be identified through the obstetric record.
 - o Conjunctivitis, defined as the presence of swollen eyelids and pus in eyes, will be identified during the care visit by the follow-up nurse/midwife.
 - o Pneumonia, defined as cough or difficult breathing plus at least one of the following: Fast breathing, Lower chest wall indrawing. In addition, either crackles or pleural rub may be present on chest auscultation.
 - o We will also ask mothers about prior neonatal symptoms and review the obstetric record.
- Maternal outcomes
 - o CT and NG infections: The prevalence of maternal CT/NG infections will be assessed among participants in the testing group at baseline and during the third trimester.
 - o The incidence of infections between baseline and follow-up in the testing group.
 - o Individual cytokines and groups of cytokines associated with mother-to-child transmission of CT/NG, preterm birth, and low birth weight.
- Economic outcomes
 - o The total cost of the CT/NG test and treatment intervention for asymptomatic pregnant women.
 - o The costs per woman tested, treated, and cured; and the incremental costs per adverse neonatal outcome averted (e.g. neonatal CT/NG infections, preterm birth, and low birth weight) comparing the testing intervention with syndromic management.

Statistical analysis

Prevalence of each STI will be measured as the proportion of individuals testing positive for a given STI divided by the number of individuals tested at each time point. Exact binomial 95% confidence intervals for prevalence will be estimated. Incident infections will be identified when a participant tests negative for an STI during her first ANC visit and positive for an STI during follow-up visits. Time at risk will be the length of time between the first test date and the positive test date. Correlates of CT/NG infections will be identified using both bivariate analyses and multivariate analyses.

Our primary outcome (mother-to-child transmission of CT and NG) and secondary outcomes (composite of preterm birth and/or low birth weight, and prevalence of maternal CT/NG infection at delivery) will be assessed using intention to treat analysis at the clinic level. We will conduct both unadjusted and adjusted analyses, including risk factors for maternal STI and neonatal infection that may be imbalanced between the testing and standard-of-care clinics. Effect measures will be estimated with 95% confidence intervals. All analyses will be carried out using the latest version of Stata statistical software (17.0 or higher; College Station, TX, USA).

To assess immune/inflammatory markers, multiple logistic regression models will be developed in an iterative process to identify individual cytokines and groups of cytokines associated with mother-to-child

transmission of CT/NG, preterm birth, and low birth weight. Additionally, we will identify plasma cytokine signatures that classify study participants with or without preterm birth/low birth weight infants.(1) We will define three equal frequency tertiles or “bins” (low, medium, and high), using all plasma samples. Next, we will use the VSURF R package, a random forest method to select the most predictive cytokines to differentiate samples from participants with and without preterm birth/low birth weight infants.(2) From these, we will build a decision tree to classify the samples. To better calibrate the accuracy of the decision tree, we will perform permutation testing.

To estimate the budget impact of CT/NG testing among asymptomatic pregnant women, we will combine the total recurrent costs with capital, training, and start-up costs. Next, we will build a decision analytic model to estimate the cost per pregnant woman tested, tested positive, treated, and cured by time of delivery. If the intervention is effective, we will calculate the incremental costs per adverse neonatal outcome averted (e.g. neonatal CT/NG infections, preterm birth, and low birth weight) comparing the testing intervention with syndromic management. We will also estimate a cost-effectiveness ratio (ICER, difference in costs divided by difference in health outcomes), representing the change in costs per averted DALYs associated with preterm birth/low birth weight infants.

We will also perform a probabilistic uncertainty analysis where parameters are randomly sampled from probabilistic distributions to generate 10,000 parameter sets. For each parameter set, the model will run and produce a distribution of outcomes. We will provide the means and 95% confidence intervals for all cost and health outcomes. If the intervention is effective, we will also calculate mean incremental cost-effectiveness ratios (ICER; \$/ DALY averted) compared to syndromic management, assessing cost-effectiveness under a willingness-to-pay threshold informed by the WHO's Gross Domestic Product / capita threshold, which was US\$7,961 in Botswana 2019. We will also calculate the probability that the scenarios are cost-effective by assessing the proportion of ICERs that fall below the willingness to pay threshold.(3)

Sensitivity analyses will be conducted through one-way and multi-way methods to identify key cost drivers and assess how changing parameters impacts the overall costs and per patient cost of each strategy.(4)

Sample size

The sample size of 500 participants was determined to have sufficient power to detect a difference in rates of vertical transmission of CT and NG based on 1) the prevalence of CT and/or NG among pregnant women in Botswana (10%),(5) and 2) the risk for vertical transmission of CT/NG to newborn infants during parturition (50%).(49-52). Antenatal CT/NG testing and treatment is expected to reduce vertical transmission by over 85%, from 5% in the control to 0.7% in the intervention group.(49, 50) When accounting for a 7% loss to follow-up rate, 250 women per arm will yield N=232 evaluable subjects. With N=232 evaluable samples per arm, we achieve 80.7% power to detect a 4.3% absolute difference in our primary endpoint, which is the proportion of vertical transmission of CT/NG, between the two groups, using a one-sided Fisher's Exact test, at a 0.05 significance level.

Methods for minimizing bias

Enrollment statistics, including total number of women attending their first antenatal clinic visit, total enrolled, total ineligible, and total who declined to participate, will be recorded in a weekly tally sheet and presented at bimonthly study meetings. Participant characteristics, such as sociodemographic characteristics, gestational age, HIV infection status, syphilis test results, obstetric history (e.g. history of preterm birth), in the testing and standard-of-care clinics will be monitored and compared to assess balance. Attrition will also be monitored and attrition bias will be assessed on a monthly basis.

Data Management

Data will be collected and managed using REDCap electronic data capture tools hosted at the Botswana Harvard AIDS Institute Partnership (BHP). REDCap (Research Electronic Data Capture) is a secure, web-based software platform designed to support data capture for research studies, providing 1) an intuitive interface for validated data capture; 2) audit trails for tracking data manipulation and export procedures; 3) automated export procedures for seamless data downloads to common statistical packages; and 4) procedures for data integration and interoperability with external sources.

Data will be entered offline at study clinics into CRFs on the REDCap mobile application on study tablets. At the end of each working day, data will be checked for any errors, discrepancies and missing data

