Title: The diagnosis and treatment of *Chlamydia trachomatis* and *Neisseria gonorrhoeae* in pregnant women to prevent adverse neonatal consequences.”

CT/NG to neonates; and 3(c): To assess the frequency and distribution of Sample Adequacy Control (SAC) cycle threshold ( $C_t$ ) values from the Xpert® CT/NG assay, which may be a marker of inflammation, and evaluate correlations with the transmission of CT/NG to neonates.

**Recruitment/Eligibility:** Eligibility criteria for the comparison group are identical to those in Aims 1 and 2. Data will only be collected from participants in the STI testing group.

**Specimen Collection, Transport, Processing and Storage:** A self-collected swab for cytokine measurement will be collected at the baseline, third trimester, and first postnatal care visit and stored at -80°C. A peripheral blood sample (2-4mL) will be collected at the baseline, third trimester, and postnatal study visits. The blood sample will be processed and aliquots of EDTA plasma will be stored at -80°C. The swabs and plasma samples will be transported in dry ice to Stanford University for processing. Luminex will be used to measure the concentrations of 48 cytokines in the 48-plex assay (including IL-1 $\alpha$ , IL-1 $\beta$ , IL-6, IL-7, IL-8, IL-10, granulocyte macrophage colony- stimulating factor [GM-CSF], interferon- $\gamma$  inducible protein [IP]-10, monocyte chemoattractant protein [MCP]-1, MIP-1 $\alpha$ , MIP-1 $\beta$ , and tumor necrosis factor [TNF]- $\alpha$ ). These cytokines were selected based on previously identified associations with genital infection. Additionally the pathogen-specific and SAC Ct results will be automatically generated for each self-collected vaginal sample tested using the Xpert® CT/NG assay at delivery.

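### The iterative cytokine models have no stated false-positive control or pre-set scope, and only about 1.6 transmission events are expected in the one group sampled

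*SAP*

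**What the plan says.** The SAP, under Statistical analysis, states that "multiple logistic regression models will be developed in an iterative process to identify individual cytokines and groups of cytokines" related to transmission of CT/NG, preterm birth and low birth weight. The result is also a listed secondary outcome measure, under Maternal outcomes: "Individual cytokines and groups of cytokines associated with mother-to-child transmission of CT/NG, preterm birth, and low birth weight".

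The protocol (section 3, Aim 3) gives the material to be searched:

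- **Markers:** "Luminex will be used to measure the concentrations of 48 cytokines in the 48-plex assay".
- **Vaginal swabs:** "A self-collected swab for cytokine measurement will be collected at the baseline, third trimester, and first postnatal care visit".
- **Plasma:** "A peripheral blood sample (2-4mL) will be collected at the baseline, third trimester, and postnatal study visits".
- **Population:** "Data will only be collected from participants in the STI testing group".

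The SAP then adds a second, separate analysis: "we will identify plasma cytokine signatures that classify study participants with or without preterm birth/low birth weight infants". It uses tertiles, random-forest selection and a decision tree, and ends with the only calibration against chance in the cytokine plan: "To better calibrate the accuracy of the decision tree, we will perform permutation testing".

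For the logistic models, neither document gives a significance level, a rule for entering or dropping markers, a choice of fluid or visit, a correction for multiple testing, or any internal validation.

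**The concern.** The product of this analysis is a list of cytokines called associated with an outcome. When many markers can be tried in two fluids at several visits against three outcomes, and the models are revised as results come in, some markers will appear associated by chance. Without a stated error rate the reader of the results cannot judge how many. Leaving fluid and visit open adds to this, because the choice can be made after the data are seen.

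The transmission models have a second problem. Cytokines are measured only in the group where the intervention is expected to remove almost all transmission, so there may be next to no events to model.

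Aim 3 and one secondary outcome are at stake. The primary comparison between the clinic groups is not affected.

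**Working it through.** **The plan's own figures.** The documents give no test count, significance level or error rate for the cytokine models, so there is none to reproduce. The inputs borrowed from the SAP's Sample size section do reproduce:

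- Control transmission rate: 10% prevalence × 50% risk = 5%.
- Evaluable women per arm: 250 × (1 − 0.07) = 232.5, stated as 232.
- Testing-group transmission rate: 0.7%, as stated.

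**Number of tests and expected chance findings.** Tests m = markers × fluids × visits × outcomes. Expected chance findings = m × 0.05 when no association is real. The 0.05 per test is an assumption; the SAP states that level only for the primary comparison.

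| Reading of the plan | m | m × 0.05 |
|---|---|---|
| Full grid | 48 × 2 × 3 × 3 = 864 | 43.2 |
| Without transmission | 48 × 2 × 3 × 2 = 576 | 28.8 |
| One fluid, three visits, three outcomes | 48 × 1 × 3 × 3 = 432 | 21.6 |
| Preterm birth and low birth weight, two antenatal visits | 48 × 2 × 2 × 2 = 384 | 19.2 |
| As above, the two outcomes as one composite | 48 × 2 × 2 × 1 = 192 | 9.6 |
| One fluid, one visit, three outcomes | 48 × 1 × 1 × 3 = 144 | 7.2 |
| One fluid, one visit, one outcome | 48 × 1 × 1 × 1 = 48 | 2.4 |

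On the narrowest reading the chance of at least one false positive is 1 − 0.95^48 = 91.5% if the tests are independent, and lower if they are positively correlated. The counts cover single-marker tests only; a search over groups of cytokines adds to them.

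**Spread.** Correlation between markers leaves the expected count unchanged but widens its distribution. This was simulated on the full grid with 232 women, 500 runs, no true associations, event rates of 0.7% for transmission and 15% each for preterm birth and low birth weight (the 15% is an assumption, not in the documents), and a common correlation between all marker series.

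| Correlation | Mean | Median | 95% range |
|---|---|---|---|
| 0 | 41.0 | 42 | 23 to 57 |
| 0.3 | 41.6 | 35 | 11 to 105 |
| 0.6 | 40.2 | 22 | 1 to 174 |

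**Effect of false discovery control.** In the same runs, Benjamini-Hochberg at 5% over the whole grid gave any false discovery in 2.8% to 3.8% of runs, and a mean of 0.04 to 1.3 false discoveries.

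**Transmission events.** Expected events in the sampled group: 232 × 0.007 = 1.6. With a binomial count, the chance of no event is 19.6% and of two or fewer 77.7%. Even if testing and treatment had no effect, 232 × 0.05 = 11.6 events would face 48 candidate markers.

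**The case against.** The strongest reply is that the SAP does not describe 864 tests. It describes multiple logistic models for single cytokines and groups, and states no 0.05 threshold for them. The full grid also contains cells that make little sense: postnatal samples are taken after delivery and cannot predict preterm birth or low birth weight. The transmission cells, 288 of the 864, would not reject at a clean 5% with so few events. A check with one null marker, 232 women and 0.7% risk gave about 1.8% rejection for Wald tests and 4.4% for likelihood-ratio tests. All of this stands. It is why the size must be given as a conditional range, and why the sparse-event problem is stated separately from the multiplicity problem.

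A reader might infer that dozens of chance findings are expected under the plan, or that the models will be searched at nominal significance. The documents do not support either. Both need every cell tested at 0.05, and the first also needs no true association; the SAP states none of these. Nor can one infer that the list would be mostly false positives: that share depends on the number of real associations and the power to find them, and the documents give neither.

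It can also be said that Aim 3(a) of the protocol speaks of describing concentrations in women who test positive, and that the plasma signature analysis has its own permutation test. The first is close to the descriptive report proposed below, but the SAP goes further and plans models for transmission. The second covers plasma and preterm birth or low birth weight only, and calibrates the tree, not the logistic models. Neither document labels the logistic analysis exploratory.

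**Conclusion.** The concern holds in a conditional form. As written, the plan selects cytokines by an iterative model search with no stated control of false positives and no stated validation, and reports the selection as a secondary outcome. No reading of the scope removes this.

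The expected number of chance findings runs from 2.4 (one fluid, one visit, one outcome) to about 43 (full grid), assuming 0.05 per test and no true association. The realised number could be far from the mean if the markers are correlated.

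The transmission part has a harder limit: about 1.6 expected events on the SAP's own rate, which cannot support a model search whatever correction is used. That figure rests on the assumed 0.7% and on 232 evaluable women.

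This should be changed before the cytokine analysis is run. It does not bear on the primary endpoint.

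**What to change.** Amend the SAP as follows:

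1. Name in advance the fluid, visit and outcome cells to be tested. Do not use postnatal samples as predictors of preterm birth or low birth weight.
2. Replace the iterative search with one pre-set model per cytokine per outcome in each named cell.
3. Control the Benjamini-Hochberg false discovery rate within each outcome at a level fixed beforehand, for example 10%, and report q-values. The 10% is a choice, not a derived figure; the simulation above used 5% over the whole grid, so it illustrates the method and not this exact rule.
4. Run any multi-marker selection wholly inside cross-validation or bootstrap, so that the reported performance includes the selection step.
5. Report transmission associations descriptively when events are too few to model, for example under 10. The SAP's own rate would trigger this.
6. Label the cytokine results exploratory.

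The cost is a short SAP amendment and some analysis code, with no new samples, visits or participants. The downside is that fewer markers will be declared associated.
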